**Plan for management of unplanned and/or emergent surgery:**

If a wound of a patient enrolled in the treatment arm is progressing more rapidly than expected, as determined by the wound care provider, the provider will withdraw the patient and instruct them to discontinue supplementation immediately in preparation for surgery. Additionally, all patients will be flagged as participating in this research study in EPIC with details on the supplements involved. There will be an explicit note that the PI of the study should be contacted prior to any surgical procedure to discuss the timing of the surgery and discontinuation of the supplements. If it is not possible for the patient to discontinue the supplementation 2 weeks prior to surgery, all relevant parties (PI, surgeon, anesthesia) will be notified of the patient's involvement in the study and discuss additional potential risks of surgery and a patient-specific strategy for management of these risks. The study coordinator will review the charts of patients included in the supplement arm daily and will facilitate this communication between parties, if necessary.

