### **k. Withdrawal of Subjects**

Subjects may withdraw from the study at any time. All data recorded to that point may be kept and used for data analysis.

The provider has the authority to remove any subject from the study at his/her discretion, at which time the provider will inform the subject of withdraw. Circumstances for withdraw include, but are not limited to:

- a. Failure to meet inclusion/exclusion criteria (labs, A1c, ECG parameters)
- b. Lack of compliance with supplementation
- b. Rapid progression of wound(s) which is expected to result in surgery during the 6-week study period
- c. Severe adverse effects which are possibly related to supplementation

All data recorded to the point of withdraw may be kept and used for data analysis.

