**Adverse Event (AE) and Serious Adverse Event (SAE) Reporting:**

Adverse events will be recorded at in-office visits, via study coordinator phone calls, and through manual chart review. All AEs will be reported to the wound care provider, if they are not already aware of the event. Serious adverse events will be immediately reported to all study investigators.

Patients who experience an adverse event (AE) assessed as  $\geq$  Grade 3 (and  $\geq$  Grade 2 for bone marrow and cardiovascular events) per NCI-CTCAE version 5.0^19 will discontinue use of the oral supplement, if in the treatment arm. These subjects will continue to be monitored until the AE resolves or stabilizes. AEs and SAEs will be promptly reported to the IRB and FDA, as required.

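### Section 9 mandates study withdrawal for fast-progressing supplement-arm wounds, Section 6k only permits it for any subject, and the week-6 and time-to-healing models have no rule for patients who leave

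*Combined protocol and SAP*

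**What the plan says.** Two sections deal with the same kind of event.

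- **Section 9, plan for unplanned or emergent surgery.** The condition is "If a wound of a patient enrolled in the treatment arm is progressing more rapidly than expected", as judged by the wound care provider. The consequence is that "the provider will withdraw the patient and instruct them to discontinue supplementation immediately in preparation for surgery". These are two actions, leaving the study and stopping the supplement, and both are stated as obligatory. There is no matching sentence for controls.
- **Section 6k, Withdrawal of Subjects.** "The provider has the authority to remove any subject from the study at his/her discretion". The listed circumstances include "Rapid progression of wound(s) which is expected to result in surgery during the 6-week study period", and also "Lack of compliance with supplementation" and "Severe adverse effects which are possibly related to supplementation". On data, it says only this: "All data recorded to the point of withdraw may be kept and used for data analysis".

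The endpoints that depend on later data are these:

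- Section 6e makes complete closure at 6 weeks the primary outcome and requires confirmation at two consecutive visits 2 weeks apart.
- Section 6h takes the proportion of wound closed at 6 weeks as its main modelled outcome. It adds Cox models for time to healing and rate of closure, and binary models for infection and need for surgery.
- Neither section gives an analysis set, a missing-data rule or a censoring rule for withdrawn patients.

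Under Section 6f, controls receive standard of care only, and no blinding is described.

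**The concern.** Rapid wound progression is close to the opposite of the healing endpoint, so withdrawal for that reason depends on the outcome. In the supplement arm it is required. In the control arm it is left to a provider who can know the allocation. Once a patient is withdrawn, nothing says that the week-6 wound assessment still takes place.

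If withdrawn patients were then left out, or censored as though their leaving carried no information, the supplement arm would lose poor outcomes more often than the control arm. The comparison would look better for the supplement than it is. In a pilot with 15 patients per arm, the estimate is most of what the study can offer to a later trial, so a few such losses matter.

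**Working it through.** The plan states no figure on this point, so there is none to reproduce. The only input from the documents is 15 patients per arm (Section 6c). Closure rates, progression rates and withdrawal counts are assumptions, because the documents give none. Every case below has no true treatment effect.

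**1. Binary closure, if withdrawn failures were dropped.** Let c of 15 close in each arm, with c = 3 to 6 (20% to 40%), and let k supplement-arm failures be dropped. The shift is c/(15 − k) − c/15.

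- k = 1: 3/14 − 3/15 = +1.4 points; 6/14 − 6/15 = +2.9 points.
- k = 2: 3/13 − 3/15 = +3.1; 6/13 − 6/15 = +6.2.
- k = 3: 3/12 − 3/15 = +5.0; 6/12 − 6/15 = +10.0.

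If one control failure is also dropped, the shift is c/(15 − k) − c/14. This gives 0 for k = 1, +1.6 to +3.3 for k = 2, and +3.6 to +7.1 for k = 3. It is 0 whenever equal numbers are dropped, and 0 if withdrawn patients count as not closed (c/15 in both arms).

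**2. Scale.** The standard error of the difference is √(2p(1 − p)/15). At p = 0.2 this is √(0.32/15) = 14.6 points; at p = 0.4 it is √(0.48/15) = 17.9 points. One dropped patient is therefore about 0.10 to 0.16 of a standard error (1.4/14.6 and 2.9/17.9), and three are about 0.34 to 0.56 (5.0/14.6 and 10.0/17.9).

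**3. Proportion of wound closed.** Let non-progressors average m = 0.5 to 0.8 closed, and let a share q of each arm progress with a value of 0.

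- All supplement-arm progressors dropped, all controls kept: m − m(1 − q) = qm. With q = 1/15 this is +3.3 to +5.3 points; with q = 2/15, +6.7 to +10.7.
- Control progressors dropped at half that rate: m(q/2)/(1 − q/2). With q = 1/15 this is +1.7 to +2.8 points; with q = 2/15, +3.6 to +5.7.

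**4. Time to healing.** I claim no hazard-ratio range. The plan does not say whether closure is dated at first sighting (weeks 2 or 4, if it is to be confirmed by week 6) or at confirmation (weeks 4 or 6). I solved the Cox score equation at expected counts, with a constant hazard, 20% to 40% true closure, and 10% to 30% of supplement-arm failures censored at week 2 or week 4. The apparent hazard ratio is 1.00 to 1.16 under the first dating and 1.04 to 1.34 under the second. It is 1.00 under either if these patients stay at risk to week 6.

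**The case against.** The strongest reply is that Section 9 is a surgical safety rule. Its heading concerns surgery, its action is in preparation for surgery, and it names the supplement arm because only that arm has a supplement to stop. Section 6k can be read as the general authority and Section 9 as one application of it. This stands in part. The triggers may be meant as the same one, and a reader who takes Section 9 to cover any worsening wound goes further than its context supports. Nothing shows that controls heading for surgery would be kept more often. What remains is required against permitted, in one arm only, and the fact that the requirement is to leave the study.

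A reader might also infer more than the documents support:

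- **That withdrawn patients have no primary-outcome status.** Section 6e's two-visit confirmation points to not closed for a patient withdrawn for progression. The section does not say so outright, but on that reading the closure bias is zero.
- **That withdrawn patients will be dropped.** No section says this. Section 6k allows their data to be used, and modelling need for surgery in Section 6h sits poorly with excluding patients who go to surgery.
- **That the non-compliance and adverse-effect grounds add to a bias toward the supplement.** In practice they reach only the supplement arm, but those patients need not be non-healers, so no direction is shown.
- **That the adverse-event rule in Section 9 already separates stopping the supplement from leaving the study.** It says "These subjects will continue to be monitored until the AE resolves or stabilizes", which is safety follow-up and promises no week-6 wound assessment.

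Chart review and the hospital alerts may still capture surgery. However, Section 6f ties chart review for infection and visits to participation, its one-year extension is for recurrence, and charts do not replace the week-6 PUSH assessment. Finally, supplement-only withdrawal is the extreme case, and the shifts are smaller than the sampling error.

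**Conclusion.** The point holds in a limited form. Sections 6k and 9 conflict on whether study withdrawal is required. Followed as written, they can remove week-6 wound data preferentially from supplement-arm failures. The proportion of wound closed and the time-to-healing model are the exposed analyses, because nothing says how a patient who leaves early enters them.

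Bias toward the supplement is possible, not demonstrated. Under the assumptions above it is about 3 to 11 points for proportion closed when 1 or 2 of 15 progress and only the supplement arm loses them. For closure it is 1.4 to 10.0 points if 1 to 3 failures are dropped, 0 to 7.1 if one control is dropped too, and 0 if withdrawal is equal or these patients count as not closed. The effect on the surgery comparison is uncertain, and I put no figure on it. The plan should be changed before results are seen.

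**What to change.** Reconcile Sections 6k and 9 so that stopping the supplement is separate from leaving the study, and so that one study-withdrawal rule covers both arms. The clinical rules for stopping the supplement stay with the investigators. Unless consent is withdrawn, continue the week 2, 4 and 6 wound assessments, and chart review for infection, surgery and amputation, in both arms.

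Add a short paragraph to Section 6h:

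- Analyse all randomised patients in the assigned arm.
- Count those stopped for progression or surgery as not closed, unless closure is confirmed under Section 6e.
- Keep them at risk to week 6 in the time-to-healing model, and state whether closure is dated at first sighting or at confirmation.
- For proportion closed, use the actual week-6 measurement, with a pre-stated value (for example, no reduction) if it is missing.
- Count surgeries within 6 weeks in both arms for the need-for-surgery outcome.

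The cost is protocol wording and one analysis paragraph. Section 12 already calls the bi-weekly visits standard of care, and chart review is planned for both arms. The apparent effect may come out slightly less favourable.

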## 2) Objectives / Research Aims

Chronic, non-healing foot ulcers are a common complication of diabetes that can threaten loss of limbs, shorten life expectancy, and require resource-intensive treatment. Patients who exhibit these late effects of diabetes are often medically complex and have not only a shortened life expectancy but also a lower quality of life than their non-ulcer peers. Despite the prevalence of obesity in these patients, many exhibit metabolic signs of malnutrition, malabsorption, or both. Even when direct treatment for the ulcer is ideal, if the patient does not have the metabolic building blocks or the correct macronutrient healing environment, then treatment will be futile.

To this end, we believe focused immunonutrition supplementation consisting of L-Arginine, Omega-3 fatty acids, and Vitamin C combined with quality wound care will lead to an improvement in treatment success, satisfaction, patient reported outcome measures, and limb salvage.

**Specific Aim 1:** To compare the healing process of diabetic patients with chronic, non-healing, lower-extremity wounds receiving oral immunonutrition supplementation to patients receiving traditional care.

- a. This will be addressed by performing a prospective, randomized pilot study including 30 diabetic patients with chronic lower extremity wounds, Wagner stages 1-2. Fifteen patients will receive oral immunonutrition supplementation (2 grams omega-3 fatty acids + 500 mg vitamin C + 4.5 grams L-arginine per day) in addition to current standard of care and 15 patients will receive the current standard of care only. Study participation will continue for 6 weeks.
- b. Effect of wound healing will be assessed utilizing the Pressure Ulcer Scale for Healing (PUSH) Tool 3.0 which scores ulcers based on size ( $\text{cm}^2$ ), exudate amount, and tissue type present. Plantar pressure profiles will be recorded using a Tekscan Pressure Mat and plantar weight-bearing foot images will be recorded. Additionally, patient charts will be monitored over the course of the study to identify rate of infection, surgical intervention, and amputation and for one year following completion of the study to assess ulcer recurrence rates.

**Specific Aim 2:** To assess compliance and patient satisfaction with an oral immunonutrition supplementation regimen in diabetic patients with chronic, non-healing, lower-extremity wounds.

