7. A follow-up safety visit will be conducted by the provider for patients randomized to the treatment group 6-8 weeks after the week 6 office visit. This visit is more than 5 half-lives after supplementation discontinuation and will allow for capture of adverse events that may occur after completion of dosing. The wound will be visualized during this visit. Adverse events and wound details will be documented in the patient's chart. This visit will be conducted in-office if the patient is already scheduled to see their provider within the visit window. If the patient is not scheduled to see their provider, this visit may be conducted virtually through EPIC.
8. Patient charts will be monitored throughout the patient's participation in the study for any signs of infection, unscheduled visits, calls to the provider, and/or onset of severe adverse events. Patient charts will continue to be monitored for one year following the completion of the study to assess ulcer recurrence rates.

The schedule of events is outlined below and is pictured in Appendix 1:

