Other secondary outcome variables to be modeled include the time to complete healing (Cox proportional hazards regression), rate of closure (Cox proportional hazards regression), presence of infection (binary regression), and need for surgery (binary regression). Cox proportional hazards models will be used to interpret the relative hazards between treatment conditions. The proportional hazards assumption will be checked using Schoenfeld residuals and accelerated failure time (parametric) regression models will also be evaluated. Binary outcomes will be modeled using various link functions (logit and log). Exponentiated coefficients for logit-link models will be interpreted as odds ratios, and exponentiated coefficients from log-link models will be interpreted as risk ratios. Binary outcomes may be relatively rare, and so we will also

estimated binary models using exact statistics. In addition, we will investigate bias through estimation of bias-corrected models.

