### **i. Data Management**

Data will be maintained in the Prisma Health REDCap and on a secure server with password protection. Study data and signed consent documents will be stored in a locked office in Prisma Health Orthopedics. Only authorized research members of this study can access this information. The researchers involved in this study commit to handle all information with care and to protect research subjects' identities. Study data will be de-identified after data collection and before sending to the biostatistician for data analysis. No PHI data will be published or presented.

Key data points include:

- BMI
- Demographic info (age, gender, race, ethnicity)
- ABI
- Hb-A1c
- Diabetes mellitus diagnosis
- Wound characteristics such as size, exudate amount, and tissue type (as documented by PUSH Tool 3.0) and Wagner stage
- Lab results (CMP, lipid panel, INR/PT)
- ECG results
- Plantar pressure profile readings
- Clinical photos of wound
- Current medications (throughout study participation)
- Treatment received as standard of care
- Rate of infection
- Rate of surgical intervention
- Rate of amputation
- Rate of ulcer recurrence
- Comorbidities
- VAS scores
- Compliance with supplementation
- Supplementation side effects

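### Surgery is modelled as a need but collected as operations done with no stated end date, while supplement-only rules on timing and withdrawal can make the count depend on arm

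*Combined protocol and SAP*

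**What the plan says.** **Outcome.** Section 6h lists "need for surgery (binary regression") among the other secondary outcomes to be modelled. Surgery is not one of the endpoints in section 6e.

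**Data.** The key data points in section 6i include "Rate of surgical intervention" and the amputation rate. No date of decision, referral or order for surgery is listed. Specific Aim 1 in section 2 says "patient charts will be monitored over the course of the study to identify rate of infection, surgical intervention, and amputation".

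**Window.** The same aim says "Study participation will continue for 6 weeks". No end date is given for surgery. Section 6f adds: "Patient charts will continue to be monitored for one year following the completion of the study to assess ulcer recurrence rates". The stated purpose of that extra year is recurrence, not surgery.

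**Timing of surgery.** The surgery plan in section 9 says: "the PI of the study should be contacted prior to any surgical procedure to discuss the timing of the surgery and discontinuation of the supplements". It then covers the case where the interval cannot be met: "If it is not possible for the patient to discontinue the supplementation 2 weeks prior to surgery", the investigator, surgeon and anesthesia team are told and agree an approach for that patient.

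**Withdrawal.** For a treated patient whose wound progresses faster than expected, the same plan says "the provider will withdraw the patient and instruct them to discontinue supplementation immediately in preparation for surgery". Section 6k instead lets the provider withdraw any subject, in either arm, when surgery is expected within the 6 weeks. It mentions keeping only data recorded up to withdrawal.

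**Ascertainment.** Daily chart review by the coordinator (section 9) and a safety visit 6 to 8 weeks after week 6 (section 6f, item 7) apply to the treatment arm only.

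**The concern.** A comparison of operations between arms is fair only if the chance that an indicated operation gets counted is the same in both. Here it may differ for three reasons, all of which follow from assignment and not from any effect on the wound.

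1. Controls have no supplement to stop, so the 2-week interval can delay an operation only in the treatment arm. A common 6-week cut-off does not remove this, because the date of operation can itself depend on arm.
2. Withdrawal before surgery is directed for some treated patients but discretionary for everyone else. No follow-up for surgery after withdrawal is described.
3. Charts are read more often, and an extra visit is made, in the treatment arm only.

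The first two would lower the treated count and the third could raise it. Limb salvage is among the hoped-for benefits in section 2, so readers will look at this outcome even in a pilot. With 15 patients per arm, one operation more or less visibly changes the estimate.

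**Working it through.** The protocol gives no surgery rate, effect size, alpha or power, so there is no figure of its own to reproduce. What follows is an illustration under stated assumptions.

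**Inputs from the protocol:** 15 patients per arm (section 6c); 6 weeks of participation (section 2); a 2-week interval, treatment arm only (section 9).

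**Assumptions:** no true effect; indications for surgery spread evenly over 6 weeks; operations after week 6 not counted; surgery rate p of 10%, 20% or 30%; two-sided alpha 0.05.

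**Step 1: deferral, controls operated on without delay.** If a share f of treated operations waits d weeks, those indicated in the last d weeks are missed:

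apparent risk ratio = 1 − f × d/6

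| Share deferred f | d = 2 weeks | d = 1 week |
|---|---|---|
| 25% | 1 − 0.25 × 2/6 = 0.92 | 0.96 |
| 50% | 1 − 0.50 × 2/6 = 0.83 | 0.92 |
| 100% | 1 − 2/6 = 0.67 | 0.83 |

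**Step 2: controls also wait.** With all treated operations deferred 2 weeks and a control wait of c weeks, the ratio is (4/6)/(1 − c/6). For c = 1 it is (4/6)/(5/6) = 0.80. For c = 2 it is 1.00.

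**Step 3: counts at full 2-week deferral.** Operations displaced = 15 × p × 2/6.

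| p | Expected, control | Expected, treated | Displaced | Chance of significant Fisher result favouring supplement | Same, no deferral |
|---|---|---|---|---|---|
| 10% | 1.5 | 1.0 | 0.5 | 0.5% | 0.3% |
| 20% | 3.0 | 2.0 | 1.0 | 2.4% | 0.8% |
| 30% | 4.5 | 3.0 | 1.5 | 3.9% | 0.8% |

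**Step 4: loss after withdrawal.** If shares w_T and w_C of operations are lost in the treated and control arms, the ratio is (1 − w_T)/(1 − w_C). Half lost in the treated arm only gives 0.50. Equal loss (short of total) gives 1.00. At the extreme, with all treated operations lost and no control ones, the ratio is 0, and the chance of a significant result favouring the supplement is 1.3%, 16% or 48% at p = 10%, 20% or 30%. This route is not confined to the last 2 weeks, so it can be larger than deferral.

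**Step 5: the opposite direction.** If operations found at the safety visit are counted, the treated arm is observed to 6 + 6 = 12 or 6 + 8 = 14 weeks. Controls would be observed to week 6 unless their charts are read for surgery after that.

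**Step 6: what a symmetric definition does.** Counting by date of indication removes d from the formula, so the ratio is 1.00 under the same assumptions. For operations performed, supplementation ends at week 6, so every treated patient has been off it for 2 weeks by week 8. A common window ending later than that leaves no operation pushed out by the interval.

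**The case against.** A reader might infer that the protocol holds treated operations for 2 weeks. It does not. The text is a conditional notification rule: surgery may go ahead sooner, with the risks discussed. It also concerns unplanned or emergent surgery, where waiting is least likely. The 0.67 is therefore a worst case and not an expectation.

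A reader might also infer that the supplement will falsely appear to prevent surgery. The documents do not support that either. The 6-week cut-off for surgery is inferred, since no end date is given. Closer chart review and a later visit in the treatment arm could raise its count. Time off supplement can overlap with ordinary scheduling, which controls face too. Even at full deferral a falsely significant result is unlikely (3.9% at most in Step 3).

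The strongest objection is that section 6h already speaks of need. If need is scored at the decision to operate, deferral changes nothing. That is right as far as it goes, but need is not defined and no decision date is among the key data points. What the listed data would support is a count of operations done.

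Two replies remain. Daily chart review cannot find, inside the window, an operation that has moved beyond it. And counting the extra visit only replaces one asymmetry with another. The objections limit the size and leave the direction open, but they do not make the comparison symmetric.

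**Conclusion.** The point stands as a defect in how a secondary outcome is defined and ascertained. As written, the number of operations counted can depend on arm through timing, withdrawal and intensity of follow-up.

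For deferral alone, the apparent null risk ratio lies between 0.92 and 0.67 when 25% to 100% of treated operations wait 2 weeks and controls do not wait. It returns toward 1.00 as controls wait too. These figures rest on even timing and a 6-week count. The surgery rates of 10% to 30% behind the counts are assumed. Unequal loss after withdrawal could be larger, but its extent cannot be derived from the documents. The net direction is not certain.

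The primary outcome, wound closure, is outside this point, and this is a 30-patient pilot. The harm is a distorted estimate more than a false significant finding. It should be corrected because the repair is cheap.

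**What to change.** In sections 6e, 6h and 6i:

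- Define the surgery outcome identically in both arms as the first recorded indication for surgery (decision, referral or order) within 6 weeks of randomisation, whenever the operation takes place. Record that date and the date of operation.
- Report operations performed as well, over one common fixed window that extends beyond week 6 by more than the 2-week interval. The one-year chart review already planned for all patients can supply this if its purpose is widened to include surgery.
- Count events in both arms regardless of withdrawal or stopping the supplement, and use the same chart-review schedule for this outcome in both arms. Extra safety review in the treatment arm can continue but should not feed the comparison.
- Reconcile section 6k with the surgery plan in section 9 on who is withdrawn. The clinical rule on the supplement and surgery is left unchanged.

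**Cost:** one extra date field, revised wording, and chart abstraction for surgery within a review already planned. The drawback is that indication is a judgement by a provider who knows the assignment, which is why operations performed are reported beside it.
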